### ***Final Report Signature***

The investigator or designee will sign the clinical study report for this study, indicating agreement with the analyses, results, and conclusions of the report.

The sponsor's responsible medical officer and statistician will sign/approve the final clinical study report for this study, confirming that, to the best of his or her knowledge, the report accurately describes the conduct and results of the study.

### ***Data Quality Assurance***

To ensure accurate, complete, and reliable data, Lilly or its representatives will do the following:

- provide instructional material to the study sites, as appropriate.
- provide training to instruct the investigators and study coordinators. This training will give instruction on the protocol, the completion of the CRFs, and study procedures.
- make periodic visits to the study site.
- be available for consultation and stay in contact with the study site personnel by mail, telephone, and/or fax.
- review and evaluate CRF data and/or use standard computer edits to detect errors in data collection.
- conduct a quality review of the database.

In addition, Lilly or its representatives will periodically check a sample of the subject data recorded against source documents at the study site. The study may be audited by Lilly and/or regulatory agencies at any time. Investigators will be given notice before an audit occurs.

The investigator will keep records of all original source data. This might include laboratory tests, medical records, and clinical notes. If requested, the investigator will provide the sponsor,

applicable regulatory agencies, and applicable ERBs with direct access to the original source documents.

### ***Data Collection Tools/Source Data***

An electronic data capture system will be used in this study. The site must define and retain all source records and must maintain a record of any data where source data are directly entered into the data capture system.

### ***Data Protection***

Data systems used for the study will have controls and requirements in accordance with local data protection law.

The purpose and use of subject personal information collected will be provided in a written document to the subject by the Sponsor.

### ***Study and Site Closure***

#### ***Discontinuation of Study Sites***

Study site participation may be discontinued if Lilly or its designee, the investigator, or the ERB of the study site judges it necessary for medical, safety, regulatory, or other reasons consistent with applicable laws, regulations, and GCP.

#### ***Discontinuation of the Study***

The study will be discontinued if Lilly or its designee judges it necessary for medical, safety, regulatory, or other reasons consistent with applicable laws, regulations, and GCP.

---

## Appendix 4. Blood Sampling Summary

---

This table summarizes the approximate number of venipunctures and blood volumes for all blood sampling (screening, safety laboratories, and bioanalytical assays) during the study.

### Protocol J2F-MC-OHAA Sampling Summary

Purpose	Blood Volume per Sample (mL)	Number of Blood Samples	Total Volume (mL)
Screening tests a	20.5	1	20.5
Clinical laboratory tests a,b	12.5	12	150
Pharmacokinetics b,d	3	17	51
Nerve growth factor b,d	0.5	17	8.5
Immunogenicity b,c,d	10	4	40
Pharmacogenetics	10	1	10
Non-pharmacogenetic storage samples	10	3	30
Total b,c,d			310
Total for clinical purposes (rounded up to nearest 10 mL)			310

a Additional samples may be drawn if needed for safety purposes.

b If 12 weeks is shorter than 5 half-lives of LY3478006 based on emerging pharmacokinetic data, up to 3 additional follow-up visits may be added, at each of which additional samples will be taken. An additional blood volume of 78 mL (37.5 mL for clinical laboratory tests, 9 mL for pharmacokinetics, 1.5 mL for nerve growth factor, and 30 mL for immunogenicity) would be collected if the subject attended the maximum allowed number of follow-up visits.

c In the event of drug hypersensitivity reactions (immediate or non-immediate), 3 additional samples will be collected for immunogenicity (a total additional blood volume of 30 mL [one 10-mL sample collected as close to the onset of the event as possible, one 10-mL sample collected at the resolution of the event, and one 10-mL sample collected 30 days following the event]).

d If the immunogenicity sample at the last scheduled assessment or discontinuation visit is TE-ADA positive, up to 4 additional outpatient visits may be required to monitor ADA until the signal returns to baseline (e.g., no longer TE-ADA positive) or for up to 1 year after the last dose. An additional blood volume of 54 mL (12 mL for pharmacokinetics, 2 mL for nerve growth factor, and 40 mL for immunogenicity) would be collected if the subject attended outpatient visits for 1 year after the last dose.

---

## Appendix 5. Laboratory Testing for Hypersensitivity Events

---

Laboratory testing should be performed at the time of a systemic hypersensitivity event. The management of the adverse event may warrant laboratory testing beyond what is described herein and should be performed as clinically indicated.

Laboratory testing during a systemic hypersensitivity event is not performed for diagnostic purposes. Its intent is several fold:

- To help characterize and classify systemic hypersensitivity reactions
- To meet regulatory expectations
- To improve subsequent clinical management by helping to distinguish between the various mechanistic bases of anaphylaxis

Blood samples will be obtained for laboratory testing in the presence of generalized urticaria or if anaphylaxis is suspected as follows:

- After the subject has been stabilized, obtain a sample within 1 to 2 hours of the event, however, samples may be obtained as late as 12 hours after the event as analytes can remain altered for an extended period of time. Record the time at which the sample was collected.
- Obtain a follow-up sample at the next regularly scheduled visit or after 4 weeks, whichever is later.

The following laboratory tests should be obtained, and will be assayed by a Lilly-designated laboratory:

- Tryptase

Note: if a tryptase sample is obtained more than 2 hours after the event (i.e., within 2 to 12 hours), or is not obtained because more than 12 hours have lapsed since the event, obtain urine for N-methylhistamine (NMH) testing. Note that for tryptase serum samples obtained within 2 to 12 hours of the event, urine NMH testing is performed in addition to tryptase testing. Collect the first void urine following the event. Obtain a follow up urine for NMH testing at the next regularly scheduled visit or after 4 weeks, whichever is later.

- Anti-LY3478006 antibodies (ADA) and LY3478006 concentration (PK)
  - ADA testing should include drug-specific immunoglobulin-E (IgE)
  - If a drug-specific IgE assay is not available, a commercially-available alternative test that can indicate the presence of drug-specific IgE in serum is the basophil activation test (BAT)

- Complement C3a and C5a
- Cytokines IL-6, IL-1 $\beta$ , and IL-10 (or any cytokine panel that includes these 3 cytokines)

---

## Appendix 6. Hepatic Monitoring Tests for Treatment-Emergent Abnormality

---

Selected tests may be obtained in the event of a treatment-emergent hepatic abnormality and may be required in follow-up with patients in consultation with Lilly or its designee CRP.

### Hepatic Monitoring Tests

Hepatic Hematologya	Haptoglobina
Hemoglobin	
Hematocrit	Hepatic Coagulationa
RBC	Prothrombin Time
WBC	Prothrombin Time, INR
Neutrophils	
Lymphocytes	Hepatic Serologiesa,b
Monocytes	Hepatitis A antibody, total
Eosinophils	Hepatitis A antibody, IgM
Basophils	Hepatitis B surface antigen
Platelets	Hepatitis B surface antibody
	Hepatitis B Core antibody
Hepatic Chemistrya	Hepatitis C antibody
Total bilirubin	Hepatitis E antibody, IgG
Conjugated bilirubin	Hepatitis E antibody, IgM
Alkaline phosphatase	
ALT	Anti-nuclear antibodya
AST	Alkaline Phosphatase Isoenzymesa
GGT	Anti-smooth muscle antibody (or anti-actin antibody)a
CPK	

Abbreviations: ALT = alanine aminotransferase; AST = aspartate aminotransferase; CPK = creatinine phosphokinase; GGT = gamma-glutamyl transferase; Ig = immunoglobulin; INR = international normalized ratio; RBC = red blood cells; WBC = white blood cells.

a Assayed by Lilly-designated or local laboratory.

b Reflex/confirmation dependent on regulatory requirements and/or testing availability.

---

## Appendix 7. Protocol Amendment J2F-MC-OHAA(a) Summary

### A Single Ascending Dose Study to Evaluate Safety, Tolerability, and Pharmacokinetics of LY3478006 in Healthy Subjects

---

## Overview

Protocol J2F-MC-OHAA, A Single Ascending Dose Study to Evaluate Safety, Tolerability, and Pharmacokinetics of LY3478006 in Healthy Subjects, has been amended. The new protocol is indicated by Amendment (a) and will be used to conduct the study in place of any preceding version of the protocol.

The updates to this protocol are those agreed to in Lilly's response to a clinical information request sent by the Food and Drug Administration. The overall changes and rationale for the changes made to this protocol are as follows:

- Footnote a in Section 2 has been amended to, "*Full physical examination on Day -1 and Day 85 or E/T (may include body temperature and respiratory rate). At all other time points, the examination will include at a minimum, an assessment of skin, injection site, and oral cavity*", to ensure that a basic physical examination is performed at each time point.
- Exclusion criterion [23] was added per an FDA request to Section 6.2 to exclude patients with abnormal liver function tests at screening. Exclusion criterion [29] was modified in accordance with changes made to Section 6.3.2.
- Section 6.3.2 has been amended per an FDA request to state that subjects will not be permitted to consume alcohol from 48 hours before each visit until leaving the CRU. Subjects will be advised to abstain from alcohol consumption for the remainder of the trial until their final visit.
- Section 9.4.5.2 has been amended to state that, "*Sites will have appropriate advanced cardiac life support (ACLS) trained medical staff and appropriate medical equipment including a crash cart available on site when study participants are receiving study drug. It is recommended that participants who experience a systemic hypersensitivity reaction be treated per the local standard of care*", as LY3478006 may be associated with infusion reactions and hypersensitivity reactions.

## Revised Protocol Sections

**Note:** All deletions have been identified by ~~strike-throughs~~.  
All additions have been identified by the use of underscore.

### 2. Schedule of Activities

## Study Schedule Protocol J2F-MC-OHAA

Procedure	Screening ≤28 days prior to Day 1	Study Day													Day 85 (±4)m or E/T
		-1	1	2	3	5	8	10 (±1)	15 (±1)	22 (±1)	29 (±1)	43 (±2)	57 (±2)	71 (±4)	
Informed Consent	X														
Outpatient Visit	X						X	X	X	X	X	X	X	X	X
CRU Admission		X													
CRU Discharge						X									
Medical History	X														
Height	X														
Weight	X	X													X
Physical Examination a	X	X	Predose	24 hr	X	X	X	X	X	X	X	X	X	X	X
Directed Neurological Examination	X	X		24 hr	X	X	X		X		X		X		X
Pupillometry		X				X		X			X				
ECG b	X		Predose (1, -0.5, 0 hr), end of infusion c , 3, 6, 12 hr	24 hr	48 hr	X	X	X	X	X	X	X	X		X
AED and Medication Review		X	X	X	X	X	X	X	X	X	X	X	X	X	X
Study Drug Administration e			0 hr												
Vital Signs f	X		Predose, end of infusion c , 3, 6, 12 hr	24 hr	X	X	X	X	X	X	X	X	X	X	X
Pregnancy Test g	X	X													X
Serology (Hepatitis B Surface Antigen, HIV, Hepatitis C Antibody)	X														

Abbreviations: ADA = antidrug antibody; AE = adverse event; CRU = clinical research unit; ECG = electrocardiogram; E/T = early termination; HIV = human immunodeficiency virus; hr = hour; IV = intravenous; NGF = nerve growth factor, PK = pharmacokinetics; SC = subcutaneous; TE-ADA = treatment-emergent antidrug antibody.

Note: Study procedures scheduled relative to IV dosing time are to occur from the time of the start of infusion; e.g., 3 hours postdose would be 3 hours after the start of the IV infusion.

a Full physical examination on Day -1 and Day 85 or E/T (may include body temperature and respiratory rate). At all other time points, the examination will include at a minimum, an assessment of skin, injection site, and oral cavity. Symptom-driven physical examination at all other times as deemed necessary by the investigator.

## 6.2 Exclusion Criteria

- [23] Have liver function test (aspartate aminotransferase [AST], alanine aminotransferase [ALT], alkaline phosphatase [ALP], total bilirubin [TBL]) above the upper limit of normal (ULN) at screening.
- [29] Have an average weekly alcohol intake that exceeds 21 units per week (males) and 14 units per week (females), or are unwilling to stop alcohol consumption from 48 hours prior to dosing ~~until discharge from the CRU (1 unit = 12 oz or 360 mL of beer; 5 oz or 150 mL of wine; 1.5 oz or 45 mL of distilled spirits).~~

### 6.3.2. Caffeine, Alcohol, and Tobacco

Consumption of caffeine- and xanthine-containing products is allowed, provided that the subject's consumption has been consistent for the past 30 days.

Subjects will not be permitted to consume alcohol from 48 hours before each visit until leaving the CRU. ~~Subjects will be advised to abstain from alcohol consumption for the remainder of the trial until their final visit. Subjects will not exceed their habitual alcohol consumption during the study. When not resident in the CRU, male subjects should be advised to limit alcohol consumption to no more than 21 units per week and female subjects to no more than 14 units per week, and all subjects should be advised to limit alcohol consumption to no more than 3 units in a day.~~

Subjects will not be permitted to smoke from CRU admission until discharge from the CRU.

2. ABBREVIATIONS

Abbreviations pertain to the Statistical Analysis Plan (SAP) only (not the tables, figures and listings [TFLs]).

AE	Adverse event
ADA	Antidrug antibody
ALP	Alkaline phosphatase
ALT	Alanine aminotransferase
AUC	Area under the concentration versus time curve
AUC _{0-∞}	Area under the concentration versus time curve from time zero to infinity
C _{max}	Maximum observed drug concentration
CI	Confidence interval
CL	Total body clearance of drug
CRF	Case Report Form
CRU	Clinical Research Unit
CSR	Clinical Study Report
CV	Coefficient of variation
ECG	Electrocardiogram
F	Bioavailability of drug
ICH	International Conference on Harmonisation
IV	Intravenous
MedDRA	Medical Dictionary for Regulatory Activities
MRE	Magnetic resonance elastography
NCA	Noncompartmental methods of analysis
NGF	Nerve growth factor
PK	Pharmacokinetic
pTrkA	Phosphorylated tropomyosin receptor kinase
SAP	Statistical Analysis Plan
SC	Subcutaneous
SD	Standard deviation
TBL	Total bilirubin
TE ADA	Treatment-emergent antidrug antibody

TFLs	Tables, Figures, and Listings
tTrkA	Total Tropomyosin receptor kinase
$t_{1/2}$	Half-life associated with the terminal rate constant (λ_z) in non-compartmental analysis
t_{max}	Time of maximum observed drug concentration
ULN	Upper limit of normal
V_{ss}	Volume of distribution at steady state following IV administration
V_z	Volume of distribution during the terminal phase
WHO	World Health Organization

3. INTRODUCTION

This SAP has been developed after review of the Clinical Study Protocol (final version dated 04 November 2019).

This SAP describes the planned analysis of the safety, tolerability and pharmacokinetic (PK) data from this study. A detailed description of the planned TFLs to be presented in the clinical study report (CSR) is provided in the accompanying TFL shell document.

The intent of this document is to provide guidance for the statistical and PK analyses of data. In general, the analyses are based on information from the protocol, unless they have been modified by agreement with Eli Lilly and Company. A limited amount of information concerning this study (e.g., objectives, study design) is given to help the reader's interpretation. When the SAP and TFL shells are agreed upon and finalized, they will serve as the template for this study's CSR.

This SAP supersedes the statistical considerations identified in the protocol; where considerations are substantially different, they will be so identified. If additional analyses are required to supplement the planned analyses described in this SAP, they may be performed and will be identified in the CSR. Any substantial deviations from this SAP will be agreed upon with Eli Lilly and Company and identified in the CSR. Any minor deviations from the TFLs may not be documented in the CSR.

This SAP is written with consideration of the recommendations outlined in the International Conference on Harmonisation (ICH) E9 Guideline entitled Guidance for Industry: Statistical Principles for Clinical Trials¹ and the ICH E3 Guideline entitled Guidance for Industry: Structure and Content of Clinical Study Reports².

4. STUDY OBJECTIVES

4.1 Primary Objective

To assess the safety and tolerability following single doses of LY3478006 in healthy subjects, including those of Japanese origin.

4.2 Secondary Objectives

- To assess the serum PK of LY3478006 following single intravenous (IV) or subcutaneous (SC) doses of LY3478006 in healthy subjects.
- To estimate the absolute bioavailability of LY3478006 following a single SC dose relative to a single IV dose in healthy subjects.

4.3 Exploratory Objectives

- To assess the changes in serum nerve growth factor (NGF) levels following single IV and SC doses of LY3478006 in healthy subjects.
- To assess the changes in skin phosphorylated TrkA (pTrkA) and total TrkA (tTrkA) levels following single IV and SC doses of LY3478006 in healthy subjects.

- To assess the serum PK of LY3478006 following single IV doses of LY3478006 in healthy Japanese subjects.

[figure not shown]
5. STUDY DESIGN

Study J2F-MC-OHAA is a Phase 1, subject- and investigator-blind, placebo-controlled, randomized, parallel, single-ascending dose study in healthy subjects.

Seven cohorts (Cohorts 1 to 7) of healthy subjects will be studied. In each cohort, 8 subjects will be randomized (3:1 ratio) to receive LY3478006 or placebo (6 LY3478006 subjects and 2 placebo subjects). Four of the 8 healthy subjects enrolled in Cohorts 3, 4, 5, and 6 are planned to be of Japanese origin (first generation; randomized [3:1 ratio] to receive LY3478006 or placebo). If the recruitment of Japanese subjects becomes limiting for a particular cohort, then additional non-Japanese subjects may be entered into a cohort to allow for dose escalation. Japanese subjects will subsequently be enrolled so that at least 3 Japanese subject's complete placebo and each LY3478006 dose level. In addition, it is preferred that the non-Japanese subjects also be non-Asian.

Cohorts 1 through 6 will be sequentially enrolled to test 6 single ascending dose levels of LY3478006 [CC1] or placebo administered IV. Subjects in Cohorts 1 through 6 may be dosed in at least 2 dosing groups (approximately 4 subjects in each group) on separate days. Study drug will be administered to 1 subject at a time (study drug infusion can start for a given subject after the end of infusion of the previous subject). Safety data through Day 15 postdose must be evaluated from at least 6 of 8 subjects prior to the decision to dose escalate to the subsequent cohort. Cohort 7 will be enrolled to test 1 dose level of LY3478006 [CC1] or placebo administered SC. All subjects in Cohort 7 may be dosed on a single day.

Figure 1 study design.

6. TREATMENTS

The following is a list of the study treatment names that will be used in the TFLs.

Study Treatment Name	Treatment order in TFL
Placebo IV	1
Placebo SC	2
CCI LY3478006 IV	3
CCI LY3478006 IV	4
CCI LY3478006 IV	5
CCI LY3478006 SC*	6
CCI LY3478006 IV	7
CCI LY3478006 IV	8
CCI LY3478006 IV	9

*CCI will be replaced with actual dose received by the subjects and doses will be presented in ascending order.

7. SAMPLE SIZE JUSTIFICATION

Up to 70 healthy subjects may be enrolled such that approximately 56 subjects complete the study. It is planned that 16 of these 56 subjects will be of Japanese origin (first-generation). Subjects who are randomized but not administered treatment may be replaced to ensure that enough subjects complete the study. The ethnicity of the replacement subject (Japanese or non-Japanese) should match the ethnicity of the discontinued subject, where possible.

The sample size is customary for Phase 1 studies evaluating safety and PK parameters, and is not powered on the basis of statistical hypothesis testing.

8. DEFINITION OF ANALYSIS POPULATIONS

The “Safety” population will consist of all enrolled subjects, whether or not they completed all protocol requirements.

The “Pharmacokinetic” population will consist of all subjects who received study drug and have evaluable PK data.

All protocol deviations that occur during the study will be considered for their severity/impact and will be taken into consideration when subjects are assigned to analysis populations.

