### 10.3. Statistical Analyses

Statistical analysis of this study will be the responsibility of Lilly or its designee.

Pharmacokinetic analyses will be conducted on data from all subjects who receive at least 1 dose of the IP and have evaluable PK. Safety analyses will be conducted for all enrolled subjects, whether or not they completed all protocol requirements.

Additional exploratory analyses of the data will be conducted as deemed appropriate. Study results may be pooled with the results of other studies for population PK analysis purposes to avoid issues with post-hoc analyses and incomplete disclosures of analyses.

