CRP	clinical research physician: Individual responsible for the medical conduct of the study. Responsibilities of the CRP may be performed by a physician, clinical research scientist, global safety physician or other medical officer.
CRU	clinical research unit

Ctrough	trough concentration
ECG	electrocardiogram
eCRF	electronic case report form
enroll	The act of assigning a subject to a treatment. Subjects who are enrolled in the study are those who have been assigned to a treatment.
enter	Subjects entered into a study are those who sign the informed consent form.
ERB	ethical review board
FHD	first human dose
GCP	good clinical practice
IAD	interim access to data
IB	Investigator's Brochure
ICF	informed consent form
ICH	International Council for Harmonization
informed consent	A process by which a subject voluntarily confirms his or her willingness to participate in a particular study, after having been informed of all aspects of the study that are relevant to the subject's decision to participate. Informed consent is documented by means of a written, signed and dated informed consent form.
investigational product (IP)	A pharmaceutical form of an active ingredient or placebo being tested or used as a reference in a clinical study, including products already on the market when used or assembled (formulated or packaged) in a way different from the authorized form, or marketed products used for an unauthorized indication, or marketed products used to gain further information about the authorized form.
investigator	A person responsible for the conduct of the clinical study at a study site. If a study is conducted by a team of individuals at a study site, the investigator is the responsible leader of the team and may be called the principal investigator.
IV	intravenous(ly)
NCA	noncompartmental methods of analysis
NGF	nerve growth factor
NOAEL	no-observed-adverse-effect-level
PAD	pharmacology active dose
PD	pharmacodynamic
PK	pharmacokinetic

randomize	the process of assigning subjects to an experimental group on a random basis
SAE	serious adverse event
SC	subcutaneous(ly)
screen	The act of determining if an individual meets minimum requirements to become part of a pool of potential candidates for participation in a clinical study.

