9. STATISTICAL METHODOLOGY

9.1 General

Summary statistics and figures by ethnicity (Japanese and non-Japanese) will be provided as appropriate.

Data listings will be provided for all data that is databased. Summary statistics and statistical analysis will only be presented for data where detailed in this SAP. For continuous data, summary statistics will include the arithmetic mean, arithmetic standard deviation (SD), median, min, max and N; for log-normal data (e.g. the PK parameters: area under the concentration versus time curve [AUC] and maximum observed drug concentration [C_{max}]) the geometric mean and geometric coefficient of variation (CV%) will also be presented. For categorical data, frequency count and percentages will be presented. Data listings will be provided for all subjects up to the point of withdrawal, with any subjects excluded from the relevant population highlighted. Summary statistics and statistical analyses will generally only be performed for subjects included in the relevant analysis population. For the calculation of summary statistics and statistical analysis, unrounded data will be used.

Mean change from baseline is the mean of all individual subjects' change from baseline values. Each individual change from baseline will be calculated by subtracting the individual subject's baseline value from the value at the timepoint. The individual subject's change from baseline values will be used to calculate the mean change from baseline using a SAS procedure such as Proc Univariate.

Data analysis will be performed using SAS® Version 9.4 or greater.

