9.4 Safety and Tolerability Assessments

9.4.1 Adverse events

Where changes in severity are recorded in the Case Report Form (CRF), each separate severity of the adverse event (AE) will be reported in the listings, only the most severe will be used in the summary tables. A pre-existing condition is defined as an AE that starts before the subject has

provided written informed consent and is ongoing at consent. A non-treatment emergent AE is defined as an AE which starts after informed consent but prior to dosing. A treatment-emergent AE is defined as an AE which occurs postdose or which is present prior to dosing and becomes more severe postdose.

All AEs will be listed. Treatment-emergent AEs will be summarized by ethnicity (overall, Japanese and non-Japanese), treatment, severity and relationship to the study drug. The frequency (the number of AEs, the number of subjects experiencing an AE and the percentage of subjects experiencing an AE) of treatment-emergent AEs will be summarized by ethnicity (overall, Japanese and Non-Japanese), treatment, Medical Dictionary for Regulatory Activities (MedDRA) version 22.1 system organ class and preferred term. The summary and frequency AE tables will be presented for all causalities and those considered related to the study drug by the investigator. Any serious AEs will be listed.

Discontinuations due to AEs will be listed.

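### The Safety population has no dosing condition, so a randomized but undosed subject could dilute the percentage of subjects with a TEAE

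*SAP*

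**What the plan says.** SAP section 8 states that the Safety "population will consist of all enrolled subjects, whether or not they completed all protocol requirements". Protocol section 10.3 agrees: "Safety analyses will be conducted for all enrolled subjects, whether or not they completed all protocol requirements". Protocol Appendix 1 fixes the meaning of the key word: "Subjects who are enrolled in the study are those who have been assigned to a treatment".

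SAP section 7, like Protocol section 10.1, provides for subjects who never receive study drug: "Subjects who are randomized but not administered treatment may be replaced to ensure that enough subjects complete the study".

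For the outcome, SAP section 9.4.1 says: "A treatment-emergent AE is defined as an AE which occurs postdose or which is present prior to dosing and becomes more severe postdose". It reports frequency as "the number of AEs, the number of subjects experiencing an AE and the percentage of subjects experiencing an AE", broken down by ethnicity and treatment. SAP section 9.1 ties summaries to the population: "Summary statistics and statistical analyses will generally only be performed for subjects included in the relevant analysis population".

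By contrast, SAP section 8 does put a dosing condition on the Pharmacokinetic population, which "population will consist of all subjects who received study drug and have evaluable PK data".

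**The concern.** Read together, these definitions admit a subject to the denominator of the TEAE percentage who can never enter its numerator. The primary endpoint is the frequency of SAEs and TEAEs (Protocol section 4), and the percentage of subjects affected is one of the three TEAE frequency measures in SAP section 9.4.1. The columns are small, so one such subject can visibly change a printed percentage. The injection-site reaction frequency tables (SAP section 9.4.9) are exposed in the same way.

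No other SAP text closes the gap. The last sentence of section 8 lets protocol deviations be weighed when populations are assigned, but it sets no dosing rule, and a randomized subject who is not dosed need not be a deviation. The footnote in SAP section 6 about the dose actually received is attached to the SC row and concerns its label. SAP section 6 lists nine treatment columns and none for untreated subjects. An undosed member of the Safety population must therefore either sit in a randomized column or appear in no column, and the SAP does not say which.

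**Working it through.** **Plan totals.** 7 cohorts × 8 = 56 subjects: 7 × 6 = 42 active and 7 × 2 = 14 placebo. Japanese subjects: 4 cohorts × 4 = 16. Both totals match the stated 56 and 16.

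**Column sizes if everyone planned is dosed** (SAP sections 5 and 6):
- Active dose level: 6.
- Japanese, one active IV dose in Cohorts 3 to 6: 4 × 3/4 = 3.
- Placebo IV: 6 × 2 = 12.
- Japanese Placebo IV: 4 × 1 = 4.
- Non-Japanese Placebo IV: 12 − 4 = 8.
- Placebo SC: 2.

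**Formula.** Let n be the number dosed in a column, x the number of those with a TEAE, and u the number randomized to that column but never dosed. The percentage among dosed subjects is x/n. With undosed subjects kept in the column it is x/(n+u). The relative understatement is 1 − n/(n+u) = u/(n+u). It is the same for any x ≥ 1. If x = 0, both percentages are 0.

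**Assumptions.** The documents do not give u; the table uses 1 and 2. Holding n at plan assumes that undosed subjects are replaced. Columns are assumed to follow randomized treatment.

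| Column | n | u = 1 | u = 2 |
|---|---|---|---|
| Active dose level | 6 | 1/7 = 14.3% | 2/8 = 25.0% |
| Japanese, one active dose | 3 | 1/4 = 25.0% | 2/5 = 40.0% |
| Placebo IV | 12 | 1/13 = 7.7% | 2/14 = 14.3% |
| Japanese Placebo IV | 4 | 1/5 = 20.0% | 2/6 = 33.3% |
| Non-Japanese Placebo IV | 8 | 1/9 = 11.1% | 2/10 = 20.0% |
| Placebo SC | 2 | 1/3 = 33.3% | 2/4 = 50.0% |

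**What the tables would print for u = 1.** SAP section 14.1 reports percentages as whole numbers.
- Active dose level: 1/6 (17%) becomes 1/7 (14%); 3/6 (50%) becomes 3/7 (43%).
- Japanese, one active dose: 1/3 (33%) becomes 1/4 (25%).
- Placebo SC: 1/2 (50%) becomes 1/3 (33%).
- Placebo IV: 1/12 (8%) becomes 1/13 (still 8%); 6/12 (50%) becomes 6/13 (46%).

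**Without replacement.** Replacement is allowed, not required. With 5 dosed out of 6 assigned, 1/5 = 20.0% becomes 1/6 = 16.7%, a relative understatement of 1/6 = 16.7%.

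**Study-wide ceiling.** If 56 complete, at most 70 − 56 = 14 enrolled subjects can be undosed. Protocol section 5.2 also allows replacement of subjects who drop out after dosing, and those come from the same 14 places. If all 14 were undosed, the overall percentage would be multiplied by 56/70 = 0.80. That is an extreme bound, not an expectation.

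**The case against.** The strongest reply is that no effect is demonstrated. A percentage moves only if at least one subject is randomized and never dosed, the columns follow randomized treatment, and at least one TEAE occurs in that column. The documents establish none of these. The table layouts are in a separate TFL shell document (SAP section 3) that may settle the column rule, and SAP section 9.1 itself says summaries are only generally restricted to the relevant population. The chance of an undosed subject also looks small: there is a single dose given on site, subjects are admitted on Day -1, and eligibility is confirmed before dosing on Day 1.

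There is also a reason to want a broad set. Predose skin biopsies are taken, and a predose SAE related to a procedure must be reported (Protocol section 9.2.1). An all-enrolled set captures such events.

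Much of this stands as a limit on size. It does not remove the gap. Both documents provide for undosed subjects. IV subjects are dosed one at a time, possibly on separate days, and meeting a stopping criterion ends dosing at that level. If a whole cohort is randomized before its first dose (the timing is not stated), a stop partway through would leave assigned but undosed subjects at that dose. Predose events can be kept through the listings without placing undosed subjects in a TEAE denominator. The shells may set the column rule, but the population definition belongs in SAP section 8.

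**Conclusion.** The concern holds, as a minor point. It is certain that the Safety population as written includes randomized but undosed subjects, and that they cannot contribute a TEAE. It is not certain that any reported percentage will be wrong.

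If a column with at least one TEAE is tabulated as randomized and contains one undosed, replaced subject, the relative understatement runs from 7.7% (Placebo IV, n = 12) to 33.3% (Placebo SC, n = 2). It is 14.3% at an active dose level.

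The consequence is limited. Numbers of events, numbers of subjects affected and the count-based stopping criteria do not change. No inferential safety analysis is planned (SAP section 9.4.15). Disposition and all AEs are listed, so a careful reader could find an undosed subject and recompute. SAP section 12, which reports no changes from the protocol, is correct on this point because SAP section 8 and Protocol section 10.3 agree.

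**What to change.** In SAP section 8, define the Safety population for summaries as all randomized subjects who receive any amount of LY3478006 or placebo, summarized by the treatment actually received. State that undosed subjects remain in the disposition and AE/SAE listings, so that predose and procedure-related events are still shown. Check that the TFL shells use the same rule.

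Align Protocol section 10.3 or, if the protocol is not amended, record the change in SAP section 12. The cost is one sentence, plus one entry in section 12 if needed. There is no cost in data or to subjects.
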